2. STUDY OBJECTIVES

2.1 Primary objective

Primary Objective:	Outcome Measure:
To compare the effect on 24-hour mean weighted glucose after 4 and 10 weeks of treatment of EQW plus metformin with placebo plus metformin, using data obtained by a CGM system	Change in 24-hour mean weighted glucose from baseline (Day -1/1) to Day 6 of Week 10 (Day 69/70) and to Day 6 of Week 4 (Day 27/28)

2.2 Secondary objectives

Secondary Objectives:	Outcome Measures:
To examine the intra-patient variability of the change in 24-hour mean weighted glucose at the beginning and the end of the dosing cycle (Week 10 of treatment in EQW patients), using data obtained by a CGM system	Change in 24-hour mean weighted glucose between Day 1 of Week 10 (Day 64/65) and Day 6 of Week 10 (Day 69/70) within each EQW-treated patient
To compare the effect on fasting plasma glucose (FPG) and 2-hour PPG after 4 and 10 weeks of dosing of EQW plus metformin with placebo plus metformin	Change from baseline (Day 1) to Day 6 of Week 10 (Day 70) and Day 6 of Week 4 (Day 28) in FPG Change from baseline (Day -1) to Day 6 of Week 10 (Day 69) and Day 6 of Week 4 (Day 27) in 2-hour mean weighted PPG (after the breakfast meal)
To compare the following parameters after 4 and 10 weeks of dosing between the EQW plus metformin and placebo plus metformin treatment groups, using data obtained by a CGM system: the effect on 24-hour mean amplitude of glucose excursion (MAGE) the proportion of time patients who had plasma glucose measurements of: <70 mg/dL ≥70 mg/dL and ≤180 mg/dL or >180 mg/dL	Average of change in 24-hour mean weighted glucose from baseline (Day -1/1) to Days 1 to 6 of Week 10 and Week 4 calculated. (standard deviation [SD], MAGE, “Distance travel”, “Energy”)
To compare the effect on HbA1c levels and 2-hour PPG after 4 and 10 weeks of dosing of EQW plus metformin with placebo plus metformin	Change from baseline (Day -1) to Day 6 of Week 10 (Day 69) and Day 6 of Week 4 (Day 27) in 2-hour mean weighted PPG (after the breakfast meal)

2.3 Safety objectives (Not applicable)

2.4 Exploratory objective

Exploratory Objective:	Outcome Measure:
The difference in daily 24-hour mean weighted glucose during Week 10, within and between treatment groups, will be assessed and described descriptively. In addition, qualitative similarities and differences in each treatment group in daily CGM profiles will be evaluated.	Exploratory statistical parameters like “Distance traveled”, the arch length of this curve and the other measures of “Energy” will be calculated

3. PATIENT SELECTION, ENROLLMENT, RANDOMIZATION, RESTRICTIONS, DISCONTINUATION, AND WITHDRAWAL

Each patient should meet all of the inclusion criteria and none of the exclusion criteria for this study. Under no circumstances can there be exceptions to this rule.

3.1 Inclusion criteria

For inclusion in the study patients should fulfill the following criteria:

1. Is willing and able to give written informed consent prior to any study specific procedures;
2. Has diagnosis of T2DM treated with a stable dose of metformin (≥ 1500 mg/day), as monotherapy for at least 8 weeks prior to Screening;
3. Has a body mass index (BMI) ≤ 45 kg/m²;
4. Has an HbA1c $\geq 7\%$ and $\leq 10\%$ obtained at Screening;
5. Has a fasting C-peptide concentration ≥ 1.0 ng/mL at Screening;
6. Is male or female, ages 18 to 75 years, inclusive;
7. Women of childbearing potential (WOCBP), defined as any female who has experienced menarche and who has not undergone surgical sterilization (hysterectomy or bilateral oophorectomy), must agree to use 2 medically accepted, effective methods of birth control (e.g., hormonal contraceptive, barrier contraceptive with additional spermicide, or an intrauterine device) beginning >30 days prior to study drug administration and continuing for 3 months after the end of the study;

8. Women must have a negative serum or urine pregnancy test (minimum sensitivity 25 IU/L or equivalent units of human chorionic gonadotropin [HCG]) within 24 hours prior to the start of investigational product;
9. Women must not be breastfeeding;
10. Males who are sexually active with WOCBP must be surgically sterile or using an acceptable method of contraception (defined as barrier methods in conjunction with spermicides) for the duration of the study (from the time they sign consent) and for 3 months after the last dose of study medication to prevent pregnancy in a partner;
11. Women who are not of childbearing potential (i.e., who are postmenopausal or surgically sterile) and azoospermic men do not require contraception. For this study, menopause is defined clinically as 12 months of amenorrhea in a woman over age 45 in the absence of other biological or physiological causes. In addition, women under the age of 62 must have a documented serum follicle-stimulating hormone (FSH) level >40 mIU/mL. Women treated with hormone replacement therapy (HRT) are likely to have artificially suppressed FSH levels and may require a washout period in order to obtain a physiologic FSH level. The duration of the washout period is a function of the type of HRT used:
- 1 week minimum for vaginal hormonal products (rings, creams, gels),
 - 4 week minimum for transdermal products,
 - 8 week minimum for oral products,
 - Other parenteral products may require washout periods as long as 6 months;
12. Has demonstrated good compliance with metformin XR (≥ 80 and $\leq 120\%$) during the lead-in period; and
13. Has demonstrated good compliance with the CGM device during the lead-in period, per Investigator decision.

3.2 Exclusion criteria

Patients should not enter the study if any of the following exclusion criteria are fulfilled:

1. Involvement in the planning and/or conduct of the study (applies to both AstraZeneca staff, Medpace staff, and/or staff at the study site);
2. Previous enrollment in the present study;
3. History of taking anti-hyperglycemic therapy other than metformin or metformin XR during the 8 weeks prior to Screening;

4. History of taking any DPP-4 inhibitor or pramlintide (SYMLIN) during the 12 weeks prior to Screening or during the study;
5. History of potent, inhaled, or intrapulmonary (including ADVAIR[®]) steroids known to have a high rate of systemic absorption during the 3 months prior to Screening or during the study;
6. History of prescription or over-the-counter weight loss medications during the 3 months prior to Screening or during the study;
7. Prior exposure to exenatide (including BYETTA, BYDUREON, or exenatide suspension) or any GLP-1 receptor agonist during the 6 months prior to Screening;
8. Prior exposure to dapagliflozin (FORXIGA, FARXIGA) or any sodium-glucose co-transporter 2 (SGLT-2) inhibitor during the 8 weeks prior to Screening;
9. Prior exposure to TZD during the 12 weeks prior to Screening;
10. Symptoms of poorly controlled diabetes that would preclude participation in this placebo-controlled trial, including but not limited to marked polyuria and polydipsia with greater than 10% weight loss during the last 3 months prior to Screening or other signs and symptoms;
11. History of diabetic ketoacidosis or hyperosmolar nonketotic coma;
12. Insulin therapy within 1 year of Screening (with the exception of insulin therapy during a hospitalization or use in gestational diabetes);
13. Significant cardiovascular history defined as:
 - History of myocardial infarction, coronary angioplasty or bypass graft(s), valvular disease or repair, unstable angina pectoris, transient ischemic attack, or cerebrovascular accidents within 6 months prior to study entry. Congestive heart failure defined as New York Heart Association stage III and IV and/or known left ventricular ejection fraction of $\leq 40\%$;
14. Repeated intermittent oral or inhaled corticosteroid treatment for periods lasting longer than 7 consecutive days during the 8 weeks prior to Screening. Patients receiving stable doses of replacement corticosteroid therapy for the 4 weeks prior to Screening may be enrolled;
15. Repeated intermittent thyroid replacement treatment (patients receiving stable doses of thyroid replacement for a minimum of 2 months prior to Screening may be enrolled);

16. Repeated intermittent anti-hypertensive agent treatment (patients receiving stable doses of anti-hypertensive for a minimum of 2 months prior to Screening may be enrolled);
17. Repeated intermittent anti-depressant treatment (patients receiving stable doses of antidepressants for a minimum of 2 months prior to Screening may be enrolled);
18. History of unstable or rapidly progressing renal disease, or severe renal impairment (creatinine clearance <30 mL/min);
19. History of alcohol or drug abuse within the previous 1 year;
20. Unstable major psychiatric disorders, as determined per the Investigator's discretion;
21. Immunocompromised individuals such as patients who have undergone organ transplantation or patients diagnosed with human immunodeficiency virus;
22. History of hemoglobinopathies (sickle cell anemia or thalassemias, sideroblastic anemia);
23. Donation of blood or plasma to a blood bank within 3 months of Screening;
24. Administration of any other investigational drug or participation in a clinical research trial within 30 days of planned enrollment to this study;
25. History of acute pancreatitis associated or not with using an anti-diabetic drug therapy;
26. Has severe gastrointestinal disease, including gastroparesis;
27. Has acute or chronic hepatic impairment;
28. Has any condition which in the Investigator's opinion may render the patient unable to complete the study or which may pose significant risk to the patient;
29. Active liver disease and/or significant abnormal liver function defined as aspartate aminotransferase (AST) >3 × upper limit of normal (ULN) and/or alanine aminotransferase (ALT) >3 × ULN and/or serum total bilirubin >2.0 mg/dL;
30. History of positive serologic evidence of current infectious liver disease including anti-HAV (IgM), HbsAg, or anti-HCV. Subjects who may have isolated positive anti-HBs may be included;
31. Personal history or family history of medullary thyroid carcinoma or inpatients with multiple endocrine neoplasia syndrome;

32. Serum creatinine (Scr) ≥ 1.5 mg/dL (132.6 $\mu\text{mol/L}$) for males and ≥ 1.4 mg/dL (123.8 $\mu\text{mol/L}$) for females;
33. Creatine kinase $\geq 3 \times$ ULN;
34. Anemia of any etiology, defined as hemoglobin ≤ 12.0 g/dL (120 g/L) for men and hemoglobin ≤ 11.0 g/dL (110 g/L) for women;
35. Has an abnormal free T4 (Note: patients with an abnormal thyroid-stimulating hormone (TSH) value at Screening will be further evaluated by free T4);
36. Has any contraindication to therapy as outlined in the BYDUREON or metformin XR/metformin package inserts;
37. WOCBP who are unwilling or unable to use an acceptable method to avoid pregnancy for the entire study and for up to 3 months after the last dose of investigational product;
38. WOCBP using a prohibited contraceptive method;
39. Women who are pregnant or breastfeeding;
40. Women with a positive pregnancy test on enrollment or prior to investigational product administration;
41. Prisoners or patients who are involuntarily incarcerated; or
42. Patients who are compulsorily detained for treatment of either a psychiatric or physical (e.g., infectious disease) illness.

For procedures for withdrawal of incorrectly enrolled patients see Section 3.4.

3.3 Patient enrollment and randomization

Investigator(s) should keep a record, the patient screening log, of patients who entered pre-study screening.

The Investigator(s) will:

1. Obtain signed informed consent from the potential patient before any study specific procedures are performed.
2. Determine patient eligibility. See Section 3.
3. If a patient withdraws from participation in the study, then his/her enrollment/randomization code cannot be reused.

3.4 Procedures for handling incorrectly enrolled or randomized patients

Patients who fail to meet the eligibility criteria should not, under any circumstances, be enrolled or receive study medication. There can be no exceptions to this rule. Patients who are enrolled, but subsequently found not to meet all the eligibility criteria must not be randomized or initiated on treatment, and must be withdrawn from the study.

Where a patient does not meet all the eligibility criteria but is randomized in error, or incorrectly started on treatment, the Investigator should inform the AstraZeneca study physician immediately, and a discussion should occur between the AstraZeneca study physician and the Investigator regarding whether to continue or discontinue the patient from treatment. The AstraZeneca study physician must ensure all decisions are appropriately documented.

3.5 Methods for assigning treatment groups

At Screening, the site will assign each patient a unique sequential patient number and enter this number into the interactive voice response system/interactive web response system (IVRS/IWRS). The patient number will consist of the letter E and a 7 digit number (the 4 digit site number and 3 digit patient number). This number will be used for identification throughout the study and will not be used for any other participant.

Patients entering the lead-in period

At the time of entry into the lead-in period, the patients will receive a pharmacy card to obtain their metformin XR.

Patients entering the double-blind treatment period

Following completion of the lead-in period, patients eligible for double-blind treatment will be randomly assigned to 1 of the 2 treatment arms by the IVRS/IWRS in a 1:1 ratio using a blocked randomization schedule:

- EQW (BYDUREON [exenatide extended-release for injectable suspension]) + metformin XR
- Placebo injection similar to EQW + metformin XR

The treatment assignment will be balanced within each site by the IVRS/IWRS through block allocation to sites. Randomization schedules will be generated and kept by AstraZeneca. At all study visits when study medication is dispensed, each patient will be assigned a kit number by the IVRS/IWRS. Kit numbers will be recorded on the eCRF. The IVRS/IWRS will be available 24 hours per day, 7 days a week.

If a dose is missed, it should be administered as soon as noticed, provided the next regularly scheduled dose is due at least 3 days later. If the next regularly scheduled dose is due within less than 3 days, then the missed dose should be skipped. Thereafter, patients can resume their usual dosing schedule of once every 7 days (weekly).

3.6 Methods for ensuring blinding

This is a double-blind study. Patients, investigators, and study personnel will remain blinded throughout the study. The AstraZeneca US Medical Lead & External Statistician will have access to unblinded data. IVRS/IWRS will be used to manage randomization to treatment arms in a blinded manner. To ensure blinding of treatments, the placebo injection will be packaged to match the single-dose trays used for investigational product (IP) during the treatment period.

3.7 Methods for unblinding

Individual treatment codes, indicating the treatment randomization for each randomized patient, will be available to the Investigator(s) from the IVRS/IWRS. Routines for this will be described in the IVRS/IWRS user manual that will be provided to each center.

The treatment code should not be broken except in medical emergencies when the appropriate management of the patient requires knowledge of the treatment randomization. The Investigator documents and reports the action to AstraZeneca, without revealing the treatment given to patient to the AstraZeneca staff.

AstraZeneca retains the right to break the code for serious adverse events (SAEs) that are unexpected and are suspected to be causally related to an investigational product and that potentially require expedited reporting to regulatory authorities. Treatment codes will not be broken for the planned analyses of data until all decisions on the evaluability of the data from each individual patient have been made and documented.

3.8 Restrictions

Patients are not permitted to use acetaminophen or paracetamol during the study, as these drugs may interfere with the CGM device.

Patients are to continue metformin XR during the study. Patients should discontinue other oral anti-hyperglycemic medications at least 4 weeks prior to Screening. The intent of this study is that patients do not deviate from their metformin regimen. However, in circumstances where a patient has a fasting glucose value above 270 mg/dL for 3 consecutive visits then the dose of metformin XR may be increased to the maximum dose of 2000 mg. This dose may be continued for the duration of the study. If such a situation occurs that patients are still not under 270 mg/dL fasting glucose after this increase in metformin XR dose then a decision to keep the patient in the study should be made only after consultation between the Investigator and the AstraZeneca clinical research physician. The decision should be documented by a note to the Investigator's file.

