3.9.1.1 Discontinuation due to hypoglycemia or symptoms suggestive of hypoglycemia

Blinded study medication or open-label metformin XR should not be down-titrated and patients should not be discontinued from any treatment phase based on single episodes of hypoglycemia or symptoms of hypoglycemia unless clinically indicated. The assessment of a single fingerstick or central laboratory glucose value should not be the sole assessment used to determine patient discontinuation due to hypoglycemia. Clinical indications for discontinuation due to hypoglycemia may include the following:

- Symptoms suggestive of hypoglycemia (e.g., sweating, shakiness, increased heart rate, confusion, dizziness, lightheadedness, or hunger) in the absence of environmental factors known to contribute to hypoglycemia (i.e., excess physical activity, concurrent illness, or missed or delayed meal) and/or
- Documented fingerstick plasma glucose values ≤ 50 mg/dL (2.8 mmol/L) on multiple occasions (2 or more occasions).

A patient may also be discontinued from the study due to severe hypoglycemia as determined by the Investigator. **No down-titration of blinded study medication or metformin XR will be allowed at any time during the study except in cases noted in Section 7.7.**

If fingerstick glucose values are discordant from glycemc control assessed by the central laboratory or with clinical symptoms, the patient's glucose meter should be tested and the procedure for using it reviewed with the patient.

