7.7 Concomitant and other treatments

Patients will be allowed to use any other concomitant medications they require during the study except: systemic glucocorticoid therapy of greater than 14 consecutive days' duration (with the exception of topical, intraocular, and inhaled preparations).

Patients will not be allowed to use acetaminophen or paracetamol during the study, as these two drugs may interfere with the CGM device.

Patients will continue metformin XR during the study. Patients should discontinue other oral anti-hyperglycemic mediations at least 4 weeks prior to screening. The intent of this study is that patients do not deviate from their metformin regimen. However, in emergencies, it may be necessary for patients to change their dose of metformin XR. This is allowed for up to 7 consecutive days or up to 7 days within a month. If such a situation occurs more than once during the study or lasts longer than 7 consecutive days or more than 7 days within a month, a decision to keep the patient in the study should be made only after consultation between the Investigator and the AstraZeneca clinical research physician. The decision should be documented by a note to the Investigator's file.

Patients must follow the medication restrictions outlined in the inclusion and exclusion criteria (Section 3.1 and Section 3.2, respectively) during the study. Dosages for certain concomitant medications should remain constant during the study unless instructed otherwise by the Investigator or treating physician. Any change in regimen for any concomitant medication, including restricted concomitant medications, must be reported to the Sponsor.

Table 6 lists the prohibited medications and the applicable time frames for this study.

Table 6 Restricted medications

Restricted medication/class of drug	Usage
Anti-hypertensive agents	Patient must either not be treated with or has been on a stable treatment regimen for a minimum of 2 months prior to Screening.
Thyroid replacement therapy	Patient must either not be treated with or has been on a stable treatment regimen for a minimum of 2 months prior to Screening.
Anti-depressant agents	Patient must either not be treated with or has been on a stable treatment regimen for a minimum of 2 months prior to Screening.
Exenatide (including Byetta [®] , Bydureon [™] , or exenatide suspension) or any GLP-1 analog	Exposure 6 months prior to Screening is prohibited (or use of non-study products during the study).

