8.5.1 Analysis of the primary variable(s)

The primary endpoint of 24-hour mean weighted glucose will be obtained by a CGM method and calculated as the AUC from the 24-hour glucose profile, divided by 24 hours. Details on AUC computations for partially missing 24-hour glucose profiles will be described in the SAP. The changes in 24-hour mean weighted glucose from baseline (Day -1/1) to Day 5-6 of Week 10 (Day 69/70) and to Day 6 of Week 4 (Day 27/28) will be analyzed using a maximum likelihood-based mixed model repeated measures (MMRM) method. The MMRM model will include change in 24-hour mean weighted glucose as the dependent variable; treatment, HbA1c stratum ($<8.5\%$ vs. $\geq 8.5\%$), baseline 24-hour mean weighted glucose, week of visit, and treatment-by-week interaction as fixed effects, and patient and error as random effects. All post-baseline measurements (including early termination visits) of the 24-hour mean weighted glucose will be included in the analysis with no imputation of missing data other than that inherent in the MMRM model. An unstructured covariance matrix will be used for the MMRM analysis, unless the model does not converge, in which case the covariance matrix will be decided upon model convergence status and the Akaike information criterion. The least squares (LS) means, standard errors of LS means, and 2-sided 95% confidence intervals (CI) for the mean change within each treatment group and the difference between treatment groups will be presented. P-values will be provided for the comparison between treatment groups. Data normality will be evaluated. If the data require logarithm transformation to meet the normality assumption for statistical modeling, the LS mean and the corresponding 95% CI will be calculated at the log scale, and the geometric mean ratio and its corresponding 95% CI will be calculated by taking the anti-log of the corresponding values within each treatment group and for treatment comparisons. The 2 primary endpoints will be tested sequentially (Week 10 comparison will follow by the Week 4 comparison) and the family-wise Type I error will be controlled between primary and secondary endpoints. See description in Section 8.5.2.

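### The rules for changing metformin XR (3.8, 7.7) and for stopping on persistent fasting hyperglycaemia (3.9.1, Table 2 note k, 5.2.6.1) are not consistent, so sites can handle the same patient differently

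*Protocol*

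**What the plan says.** Protocol sections 3.8 and 7.7 both begin by stating that patients are meant to stay on their metformin regimen. Each then gives an exception, and neither refers to the other.

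- **Section 3.8.** The exception applies "in circumstances where a patient has a fasting glucose value above 270 mg/dL for 3 consecutive visits". The dose may then go up to 2000 mg, and "This dose may be continued for the duration of the study". Consultation with the sponsor's physician is called for only if "patients are still not under 270 mg/dL fasting glucose after this increase in metformin XR dose".
- **Section 7.7.** The exception is that "in emergencies, it may be necessary for patients to change their dose of metformin XR". On duration: "This is allowed for up to 7 consecutive days or up to 7 days within a month". If the change recurs or lasts longer, "a decision to keep the patient in the study should be made only after consultation between the Investigator and the AstraZeneca clinical research physician".
- **Section 3.9.1.1.** Down-titration is barred; none "will be allowed at any time during the study except in cases noted in Section 7.7".
- **Section 3.9.1.** Fasting fingersticks of 270 mg/dL or more on three consecutive days lead to a central-laboratory test. If that is also 270 mg/dL or more, the patient is to be discontinued.
- **Table 2 note k.** Same sequence; the patient should be discontinued.
- **Section 5.2.6.1.** Same sequence, but discontinuation is only to be considered, with a pointer back to 3.9.1.
- **Section 8.5.1.** On the primary MMRM: "All post-baseline measurements (including early termination visits) of the 24-hour mean weighted glucose will be included in the analysis".

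**The concern.** Metformin XR is the background treatment in both arms, and the primary endpoint is a glucose measure. A rule on when metformin may change is therefore also a rule on what the CGM weeks measure, and a rule on when a hyperglycaemic patient leaves decides who supplies those weeks. If the protocol gives more than one answer to either question, sites must choose.

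Three things are at stake: comparability of background therapy between patients and sites, the set of patients with Week 4 and Week 10 data, and a clear standard for judging compliance when the Evaluable population is formed (section 8.3.1). The trigger is high glucose, so if exenatide works it should be met more often on placebo, and the consequences would not be evenly shared between arms.

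**Working it through.** No figure in the plan is in dispute here. The check compares the passages and then sets the visit schedule against the CGM weeks.

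**Step 1: the rules side by side.**

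| Place | Trigger | Action | Time limit | Sponsor consultation |
|---|---|---|---|---|
| 3.8 | Fasting glucose above 270 mg/dL at 3 consecutive visits | Raise to at most 2000 mg | None; rest of study | Only if still not under 270 mg/dL |
| 7.7 | Emergencies; direction of change not stated | Change dose | 7 consecutive days, or 7 in a month | If longer, or more than once |
| 3.9.1 | Fingerstick at least 270 mg/dL on 3 consecutive days, then central laboratory at least 270 mg/dL | Discontinue (will) | n/a | None stated |
| Table 2 note k | As 3.9.1 | Discontinue (should) | n/a | None stated |
| 5.2.6.1 | As 3.9.1 | Consider discontinuing | n/a | None stated |

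**Step 2: one patient under each rule.** Take a patient on 1500 mg with fasting glucose above 270 mg/dL at Days 1, 15 and 22.

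- Under 3.8 the dose may be raised on Day 22 and kept to Day 70, which is 70 − 22 = 48 days. If glucose falls below 270 mg/dL, nobody need be consulted.
- Under 7.7 as worded, persistent hyperglycaemia is not a named ground. If the section does apply, consultation is due once the change passes 7 days.
- Under 3.9.1 and note k, if daily fingersticks were also at or above 270 mg/dL on three consecutive days and the laboratory confirms, the patient leaves.
- Under 5.2.6.1 the same finding leads only to consideration.

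The visit-based and day-based triggers are not identical, and neither strictly implies the other. They sit at nearly the same level, however, and a patient who meets one could readily meet both.

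**Step 3: can a 3.8 increase reach the primary measurement?** Section 5.1.2.3 schedules central-laboratory FPG at Screening and Days -7, 1, 15, 22, 57, 64 and 70. CGM runs on Days 21–28 and 63–70. Section 3.8 does not say which visits count; the assumption here is consecutive scheduled FPG visits, before allowing for the ±3-day window.

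| Three visits | Earliest increase | Days left to Day 70 | CGM time on raised dose |
|---|---|---|---|
| -7, 1, 15 | Day 15 | 55 | Both weeks |
| 1, 15, 22 | Day 22 | 48 | Most of the first week, all of the second |
| 15, 22, 57 | Day 57 | 13 | Second week |
| 22, 57, 64 | Day 64 | 6 | Most of the second week |

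Three of the four cases run past 7 days, and all four can cover a primary measurement day (27/28 or 69/70). A change limited to 7 days from Day 15 (Days 15–21) or Day 57 (Days 57–63) would cover neither. Which section a site follows therefore changes what is in force when the endpoint is measured.

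**Step 4: reach and direction.** Section 4.1.2 gives lead-in doses of 1500 or 2000 mg. The largest step is 2000 − 1500 = 500 mg, and patients already on 2000 mg cannot receive it. An increase used more often on placebo would lower placebo glucose and narrow the difference. Early discontinuation of hyperglycaemic patients, also likelier on placebo, would remove their later values; the MMRM keeps only what was observed.

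**The case against.** The best defence is that 3.8 and 7.7 are two separate exceptions. One concerns persistent hyperglycaemia and the other emergencies, and section 3.9.1.1 cites 7.7 as the place where down-titration is permitted, which suggests that 7.7 was not written with the 3.8 increase in mind. This is a fair reading, and it defeats a stronger claim that a reader might infer: that 7.7 caps every metformin change at 7 days, so that an increase under 3.8 violates it. The text does not support that. Section 7.7 is worded for emergencies, and going beyond 7 days leads to consultation, not prohibition. What remains is that 7.7 does not limit itself to reductions and does not except the 3.8 increase, so the reader has to supply the distinction.

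Second, 3.9.1 may remove most such patients before 3.8 could act, since fasting fingersticks are to be done daily. That limits the reach of the metformin conflict, but it exposes a sharper one: 3.8 provides for continued participation at about the level where 3.9.1 ends it. One could try to assign 5.2.6.1 to the lead-in and 3.9.1 to treatment. But 5.2.6.1 points back to 3.9.1, and 3.9.1 itself contains a Day -7 provision, so the split is not stated.

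Third, the consequences are contained. Allocation is balanced within site (3.5), so differences in site practice should not line up with treatment. Regimen changes must be reported to the sponsor (7.7), violators are identified before unblinding (8.1), and evaluability is decided before codes are broken (3.7). All of this stands. It secures blind decisions, but not a single rule to decide by.

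Finally, including all post-baseline values is a legitimate choice, and further handling of weeks after a metformin change may be in the SAP. That is accepted; the inclusion rule is not criticised here.

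**Conclusion.** The point holds as an inconsistency in the protocol's instructions. For a patient with persistent fasting glucose around 270 mg/dL, the document supports a sustained dose increase without consultation, a change that needs consultation after 7 days, mandatory discontinuation, or discontinuation to be considered, depending on the section opened. An SAP cannot settle this, because these are instructions to sites.

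The effect on the primary comparison is probably small and toward no difference. The direction rests on the assumption that exenatide lowers glucose, so that the trigger is met more often on placebo; with no treatment effect and blinded site decisions, there is no evident route to a false positive.

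A reader might also infer a calculable loss of power. The documents do not support one. It would need the share of patients raised in each arm and the glucose effect of a step of at most 500 mg, and the protocol gives neither.

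**What to change.** Reconcile sections 3.8, 3.9.1 (with Table 1), Table 2 note k, 5.2.6.1 and 7.7 into one consistent set of rules. It should state when metformin XR may be changed, in which direction, for how long and with whose agreement, and when a patient with persistent fasting hyperglycaemia is discontinued. It should use one definition of the trigger (visits or days, fingerstick or central laboratory, above or at least 270 mg/dL), and each section should cross-refer to it. Which rule is right is a clinical decision for the sponsor and is not proposed here.

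Optionally, report by arm how many CGM weeks were recorded with metformin XR off the dose held at randomization, so that readers can see how far the issue arose.

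The cost is a wording amendment and a reminder to sites. The optional count should need only dosing records that 7.5 and 7.7 already require.
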